## 7. STUDY OBJECTIVES

### 7.1 Primary objective

To evaluate the specificity of the test with recombinant tuberculosis allergen (RTA) following intradermal administration in healthy subjects 18 to 30 years of age, not belonging to the risk group for the development of tuberculosis in the regions of the Russian Federation with a favorable epidemiological situation for tuberculosis.

The specificity of the RTA test is defined as the relative frequency of subjects in a healthy population (individuals with no signs of tuberculosis infection) who have a negative test reaction (no infiltration/papule) at the injection site).

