### 7.3 Primary endpoint

- Absolute number and percentage of the volunteers with negative and positive test results with RTA (individuals with no signs of tuberculosis infection) based on the results of the assessment (measurement) of the infiltrate 72 hours after the test.

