#### 9.3.1 Assessment of specificity

Specificity is a key characteristic of a diagnostic assay, referring to its ability to correctly identify individuals without the disease.

The specificity of the RTA test is defined as the proportion of subjects who tested negative (no infiltration (papule) in the injection site) in a healthy population (i.e. without MTb exposure).

$$\text{Specificity} = \frac{\text{True negatives}}{\text{True negatives} + \text{False positives}}$$

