## 12. DATA MANAGEMENT AND STATISTICAL ANALYSIS

### 12.1. General provisions

Data on the proportion of subjects who tested negative in a population of healthy subjects who are not at risk of tuberculosis are of key importance in the development of the RTA test.

The obtained results will allow us to conclude about the significance of the RTA test in the detection of tuberculosis infection.

The NMRC TPID shall be responsible for the management of the clinical study and statistical analysis of data received from all study sites.

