### 12.4 Statistical methods

The study involves the analysis of anonymized CRF data that will be performed using an MS Excel spreadsheet:

- Study subject number;
- Enrollment date;
- Sex;
- Date of birth;
- BCG vaccination status (presence of a scar);
- Height;
- Body weight;
- Complaints;
- Body temperature;
- RR per minute;
- HR;
- BP (mmHg);

- Lung auscultation: rhonchi or crackles;
- The RTA test result (mm);
- The T-SPOT.TB assay result.

Generally accepted statistical methods will be employed to analyze the study data using Microsoft® Excel® 2016 MSO application software package (version 2109 16.0.14430.20154, 32-bit, product code: 00333-59091-97459-AA884). The use of the software is planned for statistical analysis. Two-sided statistical tests at a statistical significance level of  $p < 0.05$  will be used.

Demographic and other baseline characteristics will be presented for all patients enrolled in the study (the full analysis set population).

The Shapiro-Wilk criterion will be used to determine the normality of the distribution. Parameters that are quantitative variables (including age) will be expressed as:

- Arithmetic mean (mean);
- 95% CI for the mean;

Qualitative and categorical variables (gender, etc.) will be expressed in absolute values (n/N) and proportions (%).

The study will evaluate the specificity of the RTA test (see. Paragraph 9.3.1).

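### Does the plan need to specify a confidence interval for specificity, its only primary parameter?

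*Combined protocol and SAP*

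**What the plan says.** Section 7.1 has a single aim: "To evaluate the specificity of the test with recombinant tuberculosis allergen (RTA". The primary endpoint in section 7.3 is a count and a percentage: "Absolute number and percentage of the volunteers with negative and positive test results with RTA". Section 9.3.1 defines the estimator: "The specificity of the RTA test is defined as the proportion of subjects who tested negative", written as TN/(TN + FP). Section 12.4 then refers back to that definition: "The study will evaluate the specificity of the RTA test (see. Paragraph 9.3.1".

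The rest of section 12.4 is general:
- "Generally accepted statistical methods will be employed to analyze the study data", with Excel as the named software.
- "Two-sided statistical tests at a statistical significance level of" 0.05, tied to no particular hypothesis.
- "Parameters that are quantitative variables (including age) will be expressed as" a mean with its 95% CI.
- Categorical variables are given as n/N and a percentage, with no interval.

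Section 12.5 derives the precision of estimated specificity from the binomial variance at N = 150: SD 0.041 in the worst case and 0.024 at a true value of 0.9. It states no hypothesis, power, margin or target interval width. Section 12.1 adds: "The obtained results will allow us to conclude about the significance of the RTA test in the detection of tuberculosis infection".

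**The concern.** The sample size rests on how precisely specificity will be estimated, yet the analysis section never says that this precision will be reported. Read literally, the plan attaches a 95% CI to mean age but not to its primary result. The general significance-test sentence does not fill the gap, because no null value for specificity is given.

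The likely result makes this look worse. If true specificity is near the 99.0–99.7% cited in section 6, a result of 150 negatives out of 150 is quite possible, and the plan would allow it to be reported as a bare 100%. An analyst who reached for the normal approximation would get an interval of zero width there, and upper limits above 100% at slightly lower counts. At stake is whether readers would take the result as more certain than 150 subjects can support.

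**Working it through.** **Inputs.** N = 150 (sections 8.3 and 12.5). Planning value u = 0.9 (section 12.5). Earlier specificity of 99.0–99.7% (section 6), used only as an assumed true range. All intervals are two-sided 95%.

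**The plan's own figures.** SD = sqrt(u(1 − u)/N).
- u = 0.5: 0.25/150 = 0.00167, SD = 0.0408 (stated 0.0017 and 0.041).
- u = 0.9: 0.09/150 = 0.0006, SD = 0.0245, or 0.02449 unrounded (stated 0.024).

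Both reproduce. At 0.9 the 95% half-width is 1.96 × 0.0245 = 0.048, or 4.8 percentage points.

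**What the planned n/N already yields.** The exact (Clopper-Pearson) limits for x negatives out of n are the 0.025 quantile of Beta(x, n − x + 1) and the 0.975 quantile of Beta(x + 1, n − x), with the upper limit equal to 1 when x = n.

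| Negatives/150 | Exact | Wilson | Normal approximation |
|---|---|---|---|
| 150 | 97.57–100 | 97.50–100 | 100–100 |
| 149 | 96.34–99.98 | 96.32–99.88 | 98.03–100.64 |
| 148 | 95.27–99.84 | 95.27–99.63 | 96.83–100.50 |
| 147 | 94.27–99.59 | 94.29–99.32 | 95.76–100.24 |
| 135 | 84.04–94.29 | 84.16–93.85 | 85.20–94.80 |

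The largest gap between exact and Wilson limits in the table is at 135/150: 94.29 − 93.85 = 0.44 points. Choosing between these two sound methods hardly matters.

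**How likely the all-negative result is.** P(150/150) = u^150.
- u = 0.99: 0.221.
- u = 0.997: 0.637.
- u = 0.90: 1.4 × 10⁻⁷.

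The section 6 figures come from another population (Moscow contacts of pregnant women), with equivocal results counted as non-negative. The intervals printed there for the non-negative rate, 0.2–0.6% and 0.7–1.4%, span a specificity of 98.6–99.8%. That gives 0.986^150 = 0.12 to 0.998^150 = 0.74. The scenario is plausible under the cited results and practically excluded at the planning value.

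**Does the final n matter?** With all results negative, the exact lower limit is 0.025^(1/n): 97.6% at 150, 97.5% at 145, 97.4% at 140 and 97.0% at 120. Moderate losses from the analysed set barely change it.

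**Could an interval change a conclusion?** The plan sets no threshold, comparator or hypothesis for specificity, so an interval would have nothing to be judged against. The point estimate TN/(TN + FP) is the same with or without one.

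**The case for a change.** The strongest case for a change is that the method matters near 100%, and the plan's wording does nothing to steer the analyst. The only precision formula in the document is u(1 − u)/N, and the only software is Excel, so the normal approximation is the easy default. At N = 150 the true coverage of nominal 95% intervals is:

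| True specificity | Normal approximation | Wilson | Exact |
|---|---|---|---|
| 0.90 | 92.6% | 96.0% | 97.2% |
| 0.99 | 77.8% | 93.5% | 98.2% |
| 0.997 | 36.3% | 92.5% | 98.9% |

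These figures are right, and the normal approximation would be a poor choice here. It also stands that the interval for a mean in section 12.4 does not cover a binary result, and that no sentence commits to an interval for specificity.

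The objection fails because it criticises a choice the plan does not make. Section 12.5 uses the binomial variance to plan N, not to construct an interval. A zero-width interval or an upper limit above 100% is visibly wrong and would hardly pass as a generally accepted method. Section 6 shows 95% intervals for earlier proportions with this same test, so the idea is already in the authors' practice. Any reader given n/N can also compute the interval.

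The sentence in section 12.1 does not strengthen the case. Significance there can equally mean the general importance of the test, and no criterion on specificity is attached to it.

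**Conclusion.** No change follows. Section 12.4 is silent on an interval for specificity, and stating one would have been tidier. But the plan as written yields the right estimate, reports the numbers from which the interval follows directly, and has no decision that the interval could affect. The sample-size arithmetic is correct. Exact and Wilson intervals agree to within about 0.4 points over the outcomes checked, and an all-negative result would carry a lower limit near 97.5% by either.

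This rests on two assumptions: that n/N is reported, as sections 7.3 and 12.4 promise, and that analysts do not use the normal approximation near 100%, which nothing in the plan asks them to do.

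Two neighbouring points are separate and are not settled here. Section 8.1 words specificity as agreement with T-SPOT.TB, unlike sections 7.1 and 9.3.1; because only T-SPOT.TB-negative volunteers are enrolled, the number is probably the same. Sections 9.2.1 and 12.3 describe the analysed set differently, which concerns the denominator rather than the interval.

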## **12.5 Sample size determination**

The sample size to assess the test specificity was initially estimated as the relative frequency in a binomial distribution.

For N patients, the variance of the estimated specificity is calculated as  $\text{Var}(\hat{u}) = u(1-u)/N$ , where u is (unknown) the true specificity. For a fixed value N  $\text{Var}(\hat{u})$  reaches its maximum at  $u = 0.5$ . With  $N = 150$ , this maximum is  $0.25/N = 0.0017$ , which corresponds to standard deviation (SD)  $(\hat{u}) = \sqrt{(\text{Var}(\hat{u}))} = 0.041$ . Since true specificity is expected to be higher than 0.5, an SD of 0.041 would be the worst-case scenario. With a more realistic value of true specificity of 0.9 (specificity in studies to assess the specificity of RTA was >90%), the corresponding SD would be 0.024 which is considered an acceptable estimated accuracy.

## **12.6 Interim analysis**

No interim statistical analysis is anticipated.

### **13. PROVISIONS OF THE GOOD CLINICAL PRACTICE GUIDELINES**

This protocol has been written in compliance with the ICH guidelines, Section E6 of the ICH and Section E2A of the ICH, the EU directives 2001/20/EC and 2005/28/EC of the European Parliament (including the relevant guidance), and the National Standard of the Russian Federation GOST R 52379-2005 “Good Clinical Practice.”

The study will be conducted in compliance with the principles of the Declaration of Helsinki (Appendix 6).

#### **13.1 Study Participant Information and Informed Consent Procedure**

The subjects are informed about the study verbally and in writing, with clear explanations regarding the procedures, potential risks, and benefits of the study. The subjects will be given sufficient time (at least 24 hours) to decide whether to participate in the study.

The informed consent must be signed and dated by the subject. A volunteer can be screened (Visit 0) and participate in the study only after signing informed consent.

The written information and informed consent form shall be approved by the relevant LEC before administration.

#### **13.2 Submission and approval of the application to the LEC**

The application file will be submitted to the LEC of the NMRC TPID for approval. Enrollment of subjects will not begin until the study has been approved by this authority.

The NMRC TPID is responsible for submitting the study application to the LEC.

#### **13.3 Protection of personal data of study subjects**

The Responsible Investigator of the study site shall be responsible for assigning an individual number to a volunteer after he or she signed the voluntary informed consent. Screening failures should be documented in the Visit 0 CRF, including reasons for exclusion or non-inclusion.

Voluntary informed consents and the Visits 0–3 CRFs must be signed by the Responsible Investigator of the study site to verify the accuracy of the entries.

Only the individual participant number must be included in the CRF. A CRF should be always identifiable by the respective voluntary informed consent.

Subjects should be aware of and agree to the following information:

- After the end of the clinical study (i.e. after the Last Volunteer Out date), the Principal Investigator will be keeping the voluntary informed consent forms and Visit 0–3 CRFs for at least 15 years.
- After the end of the clinical study, the voluntary informed consent forms and Visit 0–3 CRFs should be available to the LEC or other regulatory authorities for at least 15 years, if required for the inspection.

#### **13.4 Investigator responsibilities**

By signing this protocol, the Principal Investigator and the Responsible Investigator(s) of study sites shall bear overall responsibility to perform the clinical study in compliance with the protocol, GCP principles, and other relevant national normative documentation to ensure complete and accurate documenting of all data, including all AEs documented in CRFs, and to notify the NMRC

TPID immediately about serious AEs as per the procedures described in Section 11 of this protocol.

### **13.5 Curriculum vitae and registration of study staff**

The NMRC TPID must have up-to-date, dated, and signed Russian versions of CVs of the Clinical Study Leader, Responsible Investigators, etc., involved in the study.

### **13.6 Training**

The Principal Investigator shall bear overall responsibility to ensure that the study staff in all study sites has appropriate qualifications before the study commencement.

The Clinical Study Leader shall bear responsibility to provide training courses on general GCP issues, such as safety procedures, reporting of suspected serious adverse reactions including SUSARs, informing subjects, creating CRF entries, handling of diagnostic investigational medicinal products, randomization procedures, blinding and unblinding procedures, etc. If necessary, Responsible Investigators of the study site provide training sessions on the RTA test technique, etc.

### **13.7 Monitoring**

The Responsible Investigator from the NMRC TPID will oversee the conduct of the clinical study in the study sites. Scope of inspection includes:

- Compliance with protocol requirements
- Appropriate resources, equipment, and staff
- Accuracy of the completion of CRFs
- Concordance between the CRF and source data
- Proper storage conditions of the product at the study site
- Proper storage conditions of the Investigator's File at the study site

Any issue is discussed and resolved with the Investigator or designated study staff. The oversight of the clinical study will be performed as per the GCP principles.

### **13.8 Audit and inspection**

The NMRC TPID has ethical, legal, and scientific obligations to oversee the conduct of the study per the protocol and GCP standards.

The NMRC TPID may perform an audit of the study site. The audit will include monitoring of the administration of products, checking the availability of necessary documents, checking the procedure of signing the Information Sheet of the Informed Consent Form, and checking the accuracy of the completion of CRFs.

The date and time of the audit shall be agreed upon with the Investigator involved.

The Investigator agrees that the NMRC TPID will monitor the proper conduct and documentation of the study during routine visits. Data irrelevant to the study should be deleted or made unrecognizable.

The Investigator consents to an audit of the study site by an auditor designated by the NMRC TPID, as well as by a representative of the relevant authorities and ethics committees to confirm

that the conduct and documentation of the study comply with the study protocol, ICH-GCP regulations, and applicable law.

The Auditor must analyze all essential documents and verify that a randomly selected sample of data entered in the CRFs concurs with source/primary data of clinical charts. Thus, the Investigator grants direct access to source data/documents and premises where the study-related procedures are performed. It may be necessary that the Investigator be present during the monitoring and audit procedures for several hours.

### **13.9 Definition and archiving of source data**

Source data are defined as all information in the original records and validated copies of the original records required to reproduce and evaluate a clinical study. The original documents are kept at the study sites. Examples of source data:

- Documents approved by the LEC
- Signed informed consent forms
- Printed results of laboratory testing
- CRFs (data entered directly into the CRF)
- Consent of the study staff to participate in the study

Copies of anonymized CRFs will be sent to the NMRC TPID by courier delivery or e-mail.

### **13.10 Definition and archiving of essential documents**

The Principal Investigator is responsible for keeping essential documents in accordance with the ICH guidelines for at least 15 years after the study completion. The end of this clinical study is defined as the Last Subject Out.

During the monitoring of the study site, the Responsible Investigator shall agree on and ensure compliance with the archiving requirements to complete the study.

#### **14. CONFIDENTIALITY OF INFORMATION AND DISCLOSURE OF INTERESTS**

All CRFs, information, and results obtained by the NMRC TPID, as well as other information, including applications for not previously published patents and manufacturing processes, are considered confidential and shall remain the exclusive property of the NMRC TPID.

An integrated statistical and clinical study report will be prepared by the NMRC TPID.

Without a written NMRC TPID approval, no clinical study data may be published, submitted, or shared, except to regulatory agencies or the LEC, before the release of an internal clinical study report.

All Investigators agree to avoid discussing third-party issues or publish any results of the study unless the NMRC TPID can provide comments.

In the case of publication of the study results in a scientific journal, the names and order of appearance of authors will be determined by the NMRC TPID.

## **15. PARTNERSHIP AGREEMENT**

The partnership agreement between the NMRC TPID and each study site should be signed before the enrollment of the first subject in the clinical study and should clearly define the rights and obligations of the parties involved.

## 16. PROTOCOL AMENDMENTS

Clinical study procedures may be changed upon agreement with the Principal Investigator and the Clinical Study Leader. If the changes are substantive, the LEC approval should be obtained before their implementation. All substantive changes should be documented as protocol amendments, and a newer protocol version should be compiled as necessary.

